This investigation is a single-group, single site, interventional study. During the lab testing when participants indicate their preference for listening in noise, and during speech performance testing, they will be blinded as to how the hearing aids are programmed. Participants will serve as their own control as DNC “off” will be a condition in which they are tested.

5 Risks and benefits of the investigational device and clinical investigation

There are minimal risks associated with both the investigational device and participating in the clinical investigation. Identified risks are no greater than those associated with the participants personal hearing aids.

The benefits of participating in the investigation include the possibility of hearing sounds not previously heard, and being able to adjust hearing aids to improve communication in noisy environments. Additionally, participation in this study will help to inform future developments and improvements in hearing device technology for this population.

The research personnel will review these risks with the subjects and answer any questions they have. Hearing aids are not a significant risk investigational device as defined in the FDA 21 CFR 812.3(m).

6 Endpoints

The primary endpoint is listening effort, which is determined by multiple measures from the same dual-task paradigm:

- 1) **Subjective rating** of the task by answering the question “How easy was it to listen?” using a visual analog scale with verbal anchors at the end points such as “It was very easy” to “It was not at all easy”.

Secondary endpoints will include the following:

- 1) **Speech Reception Thresholds** is the lowest level, in dB, in which the participant can correctly repeat key words in a sentence. The adaptive HINT-C test will be used with the noise level presented at 67 dB and the target speech signal at varying levels. SRTs will be obtained with the study devices programmed with four different SPiN programs, each one with a different DNC level. The participant's SRT with their own personal hearing aids at their user settings will serve as the control or baseline.
- 2) **Verbal response time** is the length of time it takes the participant to respond verbally to the monosyllabic words presented in noise, while also performing a visual task simultaneously.

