- 3) **Preferences for DNC “on” compared to “off”** will be measured using a forced choice scale A/B comparison. Hearing aids will be programmed with three different SPiN programs, each one with a different DNC setting (off, weak, strong). Participants will be blinded to the settings.
- 4) **Preferences for the use of Tap Control** to access BlueTooth streaming from their smartphone will be measured using a subjective questionnaire which will ask participants to rate which method they prefer: Tap Control, HA push button, or phone control.

7 Inclusion and Exclusion Criteria

Inclusion criteria:

- Children, age 10-17
- Mild, moderate, or moderate-severe binaural sensorineural hearing loss
- Native English speakers with ability to communicate verbally
- Able to read and follow directions
- Access to smartphone and willing to download the myPhonak app to personal smartphone
- Experienced hearing aid users (6+ months)

Exclusion criteria:

- Active middle ear infection
- Unable to follow verbal directions
- Unable to communicate verbally
- Unable to tolerate the physical fit of the device

8 Measurements and procedures

All analyses of the results will occur at the conclusion of the study. Speech scores and subjective questionnaire results will be collected on paper-based forms or electronically through use of a lab-owned tablet. Data from these forms will be entered into an electronic spread-sheet prior to data analysis. It will be stored in a secure Vanderbilt network folder and shared with the Sonova once data analysis is complete on a secure Sonova drive in which only the PI has been granted access.

9 Statistical design and analysis

A power analysis on the primary objective was conducted by the PI using G-Power 3.1. Using an expected effect size for this study of 0.7 (see section 6.3) and assuming a two-condition, repeated

measures study with an alpha level of 5% and a power of 80%, 19 subjects would be necessary. Assuming an attrition rate of 20%, the targeted study enrollment for the primary objective would be 23 participants.

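### Section 9: enrolling 23 with 20% attrition gives 18.4 expected completers, not the 19 stated as necessary; the effect on power is negligible

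*Combined protocol and SAP*

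**What the plan says.** The sample size is justified in Section 9 (Statistical design and analysis) of the combined protocol and SAP: "A power analysis on the primary objective was conducted by the PI using G-Power 3.1". The expected effect size is 0.7, referred to a section 6.3 that the public document does not contain. For a two-condition, repeated "measures study with an alpha level of 5% and a power of 80%, 19 subjects would be necessary". The next sentence makes the allowance for losses: "Assuming an attrition rate of 20%, the targeted study enrollment for the primary objective would be 23 participants".

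The comparison is within subject. Section 4 states: "Participants will serve as their own control as DNC “off” will be a condition in which they are tested".

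Section 9 gives no formula for the attrition step and does not say whether the test is one- or two-sided. No section gives a different target or provides for replacing children who drop out. Missing data appear only as a possible reason for departing from the statistical plan.

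**The concern.** An attrition rate is the share of those enrolled who are lost, so the enrolment target N should satisfy N × (1 − 0.20) ≥ 19. The stated target does not. Section 9 gives a required number, an attrition rate and an enrolment target as one chain of reasoning, and the last does not follow from the first two.

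What is at stake is mainly whether the sample-size statement can be reproduced. The allowance built into the target is the plan's only protection against dropout, so the attrition it can absorb should be stated correctly.

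**Working it through.** **Inputs.** Effect size 0.7, alpha 5%, power 80%, two conditions within subject, 19 required, 20% attrition, target 23 (all Section 9; the within-subject design is also in Section 4). Assumed, because the plan does not say: the 0.7 is the mean paired difference divided by the SD of the paired differences, and the test is two-sided.

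**Step 1: reproduce the 19.** Power of a paired t-test with n pairs is P(|T| > t(0.975, n − 1)), where T is noncentral t with n − 1 degrees of freedom and noncentrality 0.7 × √n.

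| n | noncentrality | power |
|---|---|---|
| 18 | 0.7 × √18 = 2.97 | 79.92% |
| 19 | 0.7 × √19 = 3.05 | 82.25% |

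The smallest n reaching 80% is 19, as the plan says. A two-level repeated-measures F test with f = 0.35 and correlation 0.5 gives the same power. A one-sided 5% test would need only 15 (82.4%), which is why the two-sided reading is used. The base number is sound, so the disagreement arises only at the attrition step.

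**Step 2: the attrition step.**
- Needed to retain 19: 19/(1 − 0.20) = 23.75, so 24.
- Expected completers from 23: 23 × 0.80 = 18.4.
- Expected completers from 24: 24 × 0.80 = 19.2.
- Losses that 23 can absorb: 23 − 19 = 4, and 4/23 = 17.4%.

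**Step 3: where 23 might come from.**
- 19 × 1.20 = 22.8, rounded up to 23.
- Rounding once, at the end: interpolating in the table, 80% power is reached at n = 18 + (80.00 − 79.92)/(82.25 − 79.92) = 18.03, and 18.03/0.80 = 22.54, rounded up to 23.
- 23.75 rounded down to 23.

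All three give 23, and the shortfall against the stated 19 is the same under each.

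**Step 4: size of the consequence.** Let each child drop out independently with probability 0.20, so that completers are binomial (N, 0.80).

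| Enrolled | P(at least 19 completers) | Power averaged over completers |
|---|---|---|
| 23 | 50.1% | 80.4% |
| 24 | 65.6% | 82.2% |

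Going from 19 completers to 18 costs 82.25 − 79.92 = 2.33 percentage points of power.

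**The case against.** The strongest reply is that nothing of substance is lost. The 19 carries 82.3% power, and that surplus over 80% absorbs the missing fraction of a child. This stands, and it rules out the stronger reading that the trial would finish below its stated power. That reading holds only if 18.4 is cut to 18, which gives 79.9%; the average with 23 enrolled is 80.4%. The plan's inputs cannot support a distinction between 79.9% and 80% in any case: sidedness and the basis of the 0.7 are not stated, and the primary analysis is a model of ratings on response time and DNC condition, not a paired t-test.

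A reader might also infer that 19 was multiplied by 1.20 when it should have been divided by 0.80. That is a plausible origin, but no formula is shown, and dividing the unrounded 18.03 by 0.80 also leads to 23. The documents do not establish a multiplication error.

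Nor should the 50% chance of reaching 19 completers be taken as alarming. A target of 24 reaches 19 only 66% of the time, because an attrition allowance aims at the expected number and guarantees nothing.

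What the reply does not remove is the disagreement itself. The plan names 19 as necessary, and 20% attrition from 23 does not leave 19 on expectation.

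**Conclusion.** The point holds as a minor inconsistency. The required number, the attrition rate and the target cannot all stand as written: the target is one child short, or the tolerated attrition is about 17% and not 20%. That conclusion needs only the three stated figures and the usual meaning of attrition.

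The statement that power is essentially unaffected rests further on the two-sided paired t-test, the 0.7 read as a standardised paired difference, and independent dropout at 20%. No analysis, decision rule or claim in the plan changes.

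**What to change.** Amend the attrition sentence in Section 9 and show the formula. Either version makes the figures agree:

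- Keep 23, and state that it allows up to 4 losses (about 17% attrition) while leaving 19 completers, and that at 20% attrition about 18 completers are expected, with about 80% power.
- Keep the 20% rate, and state the target as 19/0.80 = 23.75, rounded up to 24.

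The same edit can say that the test is two-sided and that 0.7 is a standardised paired difference, if that is what was used. The first version costs a slightly less favourable stated tolerance. The second costs one more child.

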This study aims to identify the preferences of older children (teens and pre-teens) for DNC settings when listening in noise, and if personalization of the DNC feature using the app contributes to reduced listening effort. Subjective preference will be evaluated using blinded A/B comparisons and listening effort will be evaluated using both a subjective slider tool (see Picou, et al 2019) and objective methods (accuracy of words correct and verbal response time for monosyllabic words). Additionally, this study will evaluate speech perception at different DNC settings, from off to strong, which will help inform best practices and recommendations for fittings of older children.

2 Objectives

The primary objective for this study is to determine if DNC "on" at a preferred setting reduces the average *self-perceived* listening effort in teens and pre-teens with mild to severe hearing loss, compared to DNC "off".

The secondary objectives are to determine:

-that DNC "on" at a preferred setting is preferred to DNC "off" when listening in loud noise for teens and pre-teens with mild to severe hearing loss.

- that the majority of teens/pre-teens prefer to use Tap Control to access Bluetooth streaming with their smartphones, compared to using HA push button or phone control.
- that speech intelligibility is maintained with DNC “on”

3 Description of the investigational device

The devices used in this investigation are the Audeo Lumity 90 RICs. The myPhonak app will also be used.

For the purposes of this section, the investigational devices will be considered the hearing aid features of Dynamic Noise Cancellation (DNC) and Tap Control, as these are the specific features being studied for this population. These features are found in the Audeo Lumity devices. DNC is a spatial noise canceller which is currently available on the Audeo Lumity 90 and 70 level devices. The DNC setting is done by the HCP within the Target programming software, or by the end-user via the myPhonak app. The options for setting it range from Off, weak (1-9), moderate (10-16) and strong (17-20).

The overall intended purpose of the device is to amplify and transmit sound of the ear and thereby compensate for impaired hearing. Tap Control enables the hearing aid user to control the access to streaming from the hearing aids via taps on the ear instead of using physical controls.

4 Design of the clinical investigation

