Listening effort will be measured by a self-report, subjective question, "How easy was it to listen?" in each condition (DNC "off" and DNC "on" at preferred setting) which will be asked following a dual-task activity. This consists of a primary task of monosyllabic word recognition and a secondary task of a physical response to a visual probe. For purposes of this study, the accuracy of the word recognition will be calculated as well as the verbal response time. A generalized linear statistical model will be used in which the ratings will be the dependent variable, which will be predicted by response time and DNC condition. If there is a significant effect of the DNC condition and the mean ratings are better for DNC on at a preferred setting, the claim that DNC reduces self-perceived listening effort can be substantiated.

A general linear statistical model will also be used to analyze the secondary endpoint of objective listening effort. The dependent variable will be response time, and the independent variables will be the type of response time (either verbal response time in repeating the word or dual task response time of a button press to a colored shape) and also the DNC setting. Random effects of participant and trial will be evaluated if the data can support the complexity of the random effects. The claim of reduced listening effort can be substantiated if the verbal response time is significantly shorter with DNC on than with DNC off.

One sided binomial tests against 50% will be used to determine if the preference for DNC on is significantly different from the preference for DNC off, for the first lab task of listening to speech in a noisy environment. Preference will be measured via a blinded A/B comparison.

Preferences for the use of Tap Control compared to other methods of accessing Bluetooth streaming will also be analyzed using a binomial test.

Deviations from this statistical plan will be documented in the final study report with justification. Possible reasons for deviation include missing data and/or violated assumptions (e.g., variance, distribution, etc).

10 Investigation Duration

This study is expected to take approximately 6 months, but will depend on the recruitment rate. The expected duration for each participant is approximately 2-4 weeks.

11 Data handling and management

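### The primary model adjusts the DNC effect for response time, a same-task outcome the plan expects DNC to shorten, so it does not test the average on/off difference in the primary objective

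*Combined protocol and SAP*

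**What the plan says.** - **Objective (section 2).** The question is whether DNC on at a preferred setting "reduces the average *self-perceived* listening effort in teens and pre-teens with mild to severe hearing loss", compared with DNC off. Nothing is to be held constant.
- **Primary model (section 9).** A generalized linear model is planned in which "the ratings will be the dependent variable, which will be predicted by response time and DNC condition".
- **Decision rule (section 9).** The claim is supported "If there is a significant effect of the DNC condition and the mean ratings are better for DNC on at a preferred setting".
- **Where response time comes from (section 6).** The primary endpoint is "listening effort, which is determined by multiple measures from the same dual-task paradigm". Verbal response time is listed as a secondary endpoint and "is the length of time it takes the participant to respond verbally to the monosyllabic words presented in noise", while a visual task is done at the same time.
- **What is expected of response time (section 9).** "The claim of reduced listening effort can be substantiated if the verbal response time is significantly shorter with DNC on than with DNC off".
- **Sample size (section 9).** "Using an expected effect size for this study of 0.7 (see section 6.3) and assuming a two-condition, repeated": the sentence continues with repeated measures, 5% alpha, 80% power and 19 subjects, and enrolment is set at 23 to allow for attrition.

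The plan gives no unadjusted primary test, no mediation aim and no reason for including response time. It does not say whether the covariate is the verbal or the button-press time, whether it enters per trial or as a mean, or whether this model has a participant term.

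**The concern.** A baseline covariate leaves the treatment contrast intact and may sharpen it. Response time here is not a baseline value. It is recorded after the DNC condition is set, in the task that the child then rates, and the plan hopes DNC will shorten it. With both terms in the model, the DNC coefficient compares ratings at equal response time. Any part of the benefit that travels with faster responding is credited to the covariate.

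Two errors are possible:

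- **In the direction the plan expects, power is lost.** A real reduction in perceived effort could be reported as not shown, and this becomes more likely the better DNC works on response time.
- **In the opposite direction, a false claim is possible.** If DNC slowed responses without changing ratings, the adjusted term would be non-zero and in favour of DNC.

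The requirement of better mean ratings checks direction only; significance still rests on the adjusted term. If those means are raw means, the two halves of the rule refer to different quantities. The text does not say.

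**Working it through.** **1. The plan's own figure.** Inputs from section 9: effect 0.7, read as the mean paired difference divided by its SD; alpha 5%, taken as two-sided because the plan does not say; power 80%. For a paired t-test the noncentrality is 0.7 × √n. At n = 19 this is 0.7 × 4.36 = 3.05, against a critical value of 2.10 on 18 df. Exact power from the noncentral t is 79.9% at n = 18, 82.3% at n = 19 and 89.4% at n = 23. So 19 is reproduced by the unadjusted two-sided paired comparison. A one-sided test would need 15.

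**2. What the planned model tests.** Assume one rating and one response-time value per participant and condition, a participant effect and an identity link. Let D be the rating improvement with DNC on and X the shortening of response time, each with SD 1; r is their correlation and m the mean of X. The DNC coefficient is then the intercept of D regressed on X:

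adjusted effect = 0.7 − r × m, with SE ≈ √(1 − r²) × √(1/n + m²/(n − 1)).

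Example with r = 0.5, m = 0.5, n = 19: the effect is 0.7 − 0.25 = 0.45. The SE is about 0.866 × √(0.0526 + 0.0139) = 0.223. The ratio is 2.02 against a critical value of 2.11 on 17 df, so power is a little under one half.

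**3. Power by simulation** (two-sided 5%, 100,000 trials per cell; 40,000 per n in the last column). The documents give neither r nor m, so both are assumptions.

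| r | m (SD) | Adjusted effect | Power, n = 19 | Power, n = 23 | n for 80% |
|---|---|---|---|---|---|
| 0.3 | 0 | 0.70 | 83% | 90% | – |
| 0.3 | 0.3 | 0.61 | 69% | 78% | 25 |
| 0.3 | 0.5 | 0.55 | 54% | 64% | 33 |
| 0.3 | 0.7 | 0.49 | 40% | 47% | 48 |
| 0.5 | 0 | 0.70 | 90% | 95% | – |
| 0.5 | 0.3 | 0.55 | 68% | 77% | 25 |
| 0.5 | 0.5 | 0.45 | 46% | 55% | 40 |
| 0.5 | 0.7 | 0.35 | 27% | 32% | 75 |

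The unadjusted test has 82% power at 19 and 89% at 23 in every row.

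**4. Smaller values, n = 19.** With r = 0.1, power is 79% at m = 0.1 and 73% at m = 0.3. With r = 0.3 and m = 0.1 it is 80%. With r = 0.5 and m = 0.1 it is 85%, slightly above the unadjusted test. With r = 0 the effect stays at 0.70, but power still falls to 76%, 70% and 63% at m = 0.3, 0.5 and 0.7, because the covariate then overlaps with the condition.

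**5. False claims when ratings do not change, n = 19.** The rule is two-sided p < 0.05 and a better raw mean with DNC on. If DNC slows responses by 0.3, 0.5 or 0.7 SD, the claim is made in 5.5%, 8% and 10% of trials (r = 0.3) or in 9.5%, 17% and 23% (r = 0.5). The unadjusted rate is 2.5%. If DNC speeds responses by 0.3 to 0.7 SD, the rate is about 1% to 4%.

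**6. Other readings of the model.**
- *Pooled, no participant term* (assumed intraclass correlation 0.3 to 0.7, between-person correlation 0 to 0.5): adjusted effect 0.67 to 0.35.
- *Trial-level response times* (assumed 25 trials per condition, trial noise 0.5 to 2 SD of the paired change): adjusted effect about 0.54 to 0.70.
- *One participant-level average across conditions*: the covariate cannot differ between on and off, so the adjusted and overall effects coincide.

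**The case against.** The best counter-argument is that the plan is too loosely worded to support one fixed reading. With trial-level response times most of the attenuation disappears, and with a participant average all of it does. If the covariate is the button-press time, the plan states no rule that it must be shorter with DNC on. Section 2 lists no response-time objective, and the section 9 rule is conditional, so the expected shortening is partly inferred. The 0.7 is referred to a section 6.3 that is not in the available text, so it cannot be checked whether it came from an adjusted analysis. The worst power figures come from one corner of an assumed grid. In the plan's hoped-for direction the error is conservative. The arithmetic also assumes an identity link, although the plan says generalized linear and the rating is a bounded scale.

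Much of this stands as a limit on size: the power figures are illustrations, and 27% and 75 completers are the extreme case. It does not remove the point. The plan adopts neither of the readings that would rescue it. With the rating asked after each condition's task, one response-time value per condition is the natural reading. Trial-level values set against a single rating would also bring pseudo-replication. The sole response-time claim rule in the plan runs one way, towards shorter with DNC on. A covariate can add precision, but a clear gain requires that DNC leaves response time nearly unchanged. The deviation clause in section 9 gives missing data and violated assumptions as possible reasons; a change of primary contrast made after seeing the data would weaken the claim.

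**Conclusion.** The concern holds. As written, the one test that decides the primary claim conditions on an outcome measured under the intervention, while the objective asks for the average on/off difference and the sample size matches that unconditioned comparison. This follows from the wording and needs no assumed figure, except that the two effects coincide if DNC does not shift response time or if the covariate is a participant average.

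The size of the harm is uncertain. Under the paired reading, with an identity link and a true effect of 0.7 SD, the cost at 19 participants runs from about 13 points of power (82% to 69%) to about 55 points (82% to 27%) over the main grid. It is only a few points, or nil, when the response-time shift is about 0.1 SD. The false-claim risk is secondary: it requires DNC to slow responses, contrary to the plan's expectation, and raw means in the decision rule.

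**What to change.** Replace the primary-model sentence and its decision rule in section 9 with wording such as:

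> The primary analysis is the within-participant difference in ratings, DNC on at preferred setting minus DNC off, tested two-sided at 5% by a paired t-test, or equivalently by a linear mixed model with DNC condition and a participant effect. The claim is substantiated if this difference is significant and favours DNC on.

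State which of the two forms is used. Label any model that adds response time as exploratory, and specify whether it uses verbal or button-press time and whether this enters per trial or as a condition mean.

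**Cost.** No new data and no change in sample size: 19 completers give 82% power for this test. The change does need an amended plan with the signatures required by section 12, and should be made before the ratings are analysed. The statistical price is small. If DNC leaves response time unchanged and the correlation is 0.3 to 0.5, dropping the covariate gives up about 1 to 8 points of power at 19 (82% against 83% to 90%). A paired t-test also departs from the generalized linear model now named; the mixed model stays closer to it.

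### The primary rating model has no participant term although each child is rated under both DNC conditions, so its DNC test lacks the error properties that the sample size assumes

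*Combined protocol and SAP*

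**What the plan says.** Section 4 sets up a within-child comparison, with the off setting among those tested: "Participants will serve as their own control as DNC". The power statement in section 9 follows that design: "Using an expected effect size for this study of 0.7 (see section 6.3) and assuming a two-condition, repeated". The same sentence then gives the error rates and the resulting number: "measures study with an alpha level of 5% and a power of 80%, 19 subjects would be necessary". After attrition, "the targeted study enrollment for the primary objective would be 23 participants".

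The primary outcome is one self-report question put in each condition, "which will be asked following a dual-task activity". The primary model is a generalized linear model in which "the ratings will be the dependent variable, which will be predicted by response time and DNC condition". The claim is accepted "If there is a significant effect of the DNC condition and the mean ratings are better for DNC on at a preferred setting".

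The only participant term is in the next paragraph of section 9, which concerns the secondary response-time endpoint: "Random effects of participant and trial will be evaluated if the data can support the complexity of the random effects". That paragraph would also support its own claim if verbal response time is shorter with DNC on.

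The plan does not state the within-child correlation of ratings, the units of the 0.7 (it points to a section 6.3 that is not in this document), or whether a row of the primary analysis is a child-condition or a trial.

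**The concern.** The design and the sample size are paired, but the primary model as written is not. A model without a participant term treats a child's two ratings as unrelated. It therefore uses the wrong variance for the DNC difference. The error can go either way, depending on how the data are laid out: the trial may miss the effect it was sized to detect, or it may declare an effect far too often.

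Response time adds a second problem. It is measured under each condition, and the plan's secondary claim is that DNC shortens it. Holding it fixed can move part of the DNC effect out of the DNC term. The primary objective in section 2 asks about DNC on versus off, not about the effect at equal response time.

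**Working it through.** **Inputs from section 9.** Effect size 0.7, alpha 5%, power 80%, n = 19, enrolment 23. **Assumed.** Two-sided test; rho from 0.15 to 0.7; the units of the 0.7 (both readings shown).

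**1. The plan's own figure.** Paired t-test with standardised paired difference 0.7: noncentrality 0.7 × √n on n − 1 degrees of freedom. For n = 19, 0.7 × √19 = 3.05 and power is 82.3%. For n = 18 it is 79.9%. So 19 reproduces under a two-sided paired analysis; two independent groups would need 33 each.

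**2. One row per child per condition, no covariate, no participant term.** Let each rating have variance σ². The model takes the variance of the DNC difference as 2σ²/n, but the true value is 2σ²(1 − rho)/n. The standard error is therefore too large by 1/√(1 − rho). Power and type I error come from simulating correlated pairs analysed as two independent groups.

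If 0.7 is a paired effect, the raw effect is 0.7 × √(2(1 − rho)). If 0.7 is a raw-SD effect, the paired effect is 0.7/√(2(1 − rho)), which is 0.54, 0.59, 0.70 and 0.90 at the four values of rho. All figures in the table are for n = 19.

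| rho | SE factor | Type I error, no participant term | Power, no participant term, 0.7 paired | Power, no participant term, 0.7 raw SD | Power, paired test, 0.7 raw SD |
|---|---|---|---|---|---|
| 0.15 | 1.08 | 3.4% | 80% | 56% | 60% |
| 0.3 | 1.20 | 2.1% | 73% | 57% | 68% |
| 0.5 | 1.41 | 0.8% | 58% | 58% | 82% |
| 0.7 | 1.83 | 0.1% | 29% | 60% | 96% |

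If 0.7 is a paired effect, the paired test has 82% power at every rho. If all 23 children complete, power without the participant term is 82%, 69% and 40% at rho 0.3, 0.5 and 0.7. It drops below 80% above rho of about 0.15 (n = 19) or 0.35 (n = 23).

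**3. One rating copied onto k trial-level rows per condition.** The model now takes the variance as 2σ²/(nk), while the true value is still 2σ²(1 − rho)/n. The ratio of true to assumed variance is k(1 − rho), and the test is anti-conservative once this exceeds 1. At rho 0.5 and k = 5 the ratio is 2.5; at k = 20 it is 10. Simulated type I error (n = 19, rho 0.5, no covariate) is about 23% and 55%.

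**4. Response time as a covariate (illustrative; the plan gives none of these inputs).** Take a paired analysis adjusted for response time, with 19 completers and a rating effect of 0.7. Suppose DNC shortens response time by 0.3, 0.5 or 0.7 paired SD.

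- Rating and response-time improvements uncorrelated: power 76%, 70% and 63%.
- Correlated 0.3: the adjusted effect is 0.7 − 0.3 × 0.3 = 0.61, 0.7 − 0.3 × 0.5 = 0.55 and 0.7 − 0.3 × 0.7 = 0.49, with power 69%, 54% and 40%.
- Correlated 0.3 but no DNC shift in response time: power 83%, so adjustment does no harm there.
- An association in the opposite direction would enlarge the adjusted effect.

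Without the participant term and with no DNC shift in response time, keeping the covariate gives 57–64% power at rho 0.5 and 30–39% at 0.7. The covariate therefore does little to make up for the missing term.

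**The case against.** The best defence is that this is under-specification, not a chosen unpaired test. Section 9 uses a linear-model label for the response-time analysis too, and that analysis may carry random effects. The list of predictors for the ratings could be fixed effects only. Sections 4 and 9 make the paired intent plain, and violated assumptions are listed as a reason for documented deviations.

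The intent stands, but the defence does not supply the term. The random-effects sentence belongs to another endpoint and, even if extended to the ratings, is conditional. The deviation clause would leave the primary model to be settled after the data are in.

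It is also fair that the loss depends on an unstated rho. At about 0.15 or below there is essentially no shortfall on the paired reading of 0.7. The steep fall to 29% comes from holding the paired effect at 0.7 while rho rises, which shrinks the raw effect from 0.83 SD at rho 0.3 to 0.54 SD at 0.7. On the raw-SD reading, power without the term is roughly flat at 56–60%.

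A reader might infer that the omission is merely conservative, so that a positive result would still be valid. The documents do not support that. Response time is recorded word by word, the plan speaks of trial effects for it, and no row unit is given, so copied rows are a live possibility. Inflation then needs neither repeated ratings nor a DNC effect that differs between children. The covariate also changes what the DNC term estimates.

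**Conclusion.** The concern holds. As written, the primary DNC test does not have the power or type I error that the paired sample size presumes. The size of the problem rests on assumptions: rho, the units of the 0.7, two-sided testing and the data layout. With one row per condition the test is conservative, and at rho 0.5 with 19 completers power is about 58% instead of 82% on either reading of the 0.7. With copied trial rows it is anti-conservative. The response-time effect is real in principle, but its size is illustrative only.

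Two stronger readings go too far. The documents do not show that inflated type I error will occur, only that the plan does not rule it out. Nor do they show that 19 is wrong: it reproduces for a paired analysis. The fault is in the stated model. This should be corrected before analysis, because the primary claim depends on this one term.

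**What to change.** In section 9:

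- Define the analysis unit as one rating per child per condition, averaging any repeats first.
- Test DNC condition in a linear mixed model with a mandatory participant random intercept. For complete pairs and non-negative rho, a paired t-test is equivalent.
- Make the test without response time primary, and report the response-time-adjusted model as supportive.
- State whether the 0.7 is a paired or a raw-SD effect, and any correlation assumed, in place of the pointer to section 6.3.

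The cost is wording only, with no new data. On the paired reading, 19 completers give 82% power and N stays as it is. If the 0.7 proves to be a raw-SD effect, the paired test has 82% at rho 0.5 but only 68% at rho 0.3, so the assumed correlation would have to be justified or N revisited.
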